9.1.4 Exploratory Endpoints

In addition to defining the MTD, the study will provide useful preliminary data concerning efficacy. Methods of assessing response will be specific to each individual patient as described in Section 5.6. In the subset of patients with radiographically measurable disease RECIST 1.1 criteria will be used.

Patients in the per protocol population will be classified as responder or non-responder and the proportion of patients exhibiting response at trial closure by any criteria will be estimated by the 90% confidence interval. Patients who experience a radiographic/tumor marker CR will undergo confirmatory laparoscopy.

Time to progression measured from study entry to documented progression of disease will be estimated by the method of Kaplan-Meier in the intent-to-treat population. Patients who withdraw from the trial prior to disease progression, are either lost to follow-up, die or begin alternative treatments prior to progression, will be censored at the date considered to be lost to follow-up, date of death, or the first day of alternative therapy.

For all efficacy endpoints, analyses will be performed overall and in the patients treated at the MTD. These analyses are primarily exploratory since the data will be from only a limited number of patients available for the study.

As a first approach to addressing our exploratory aim of evaluating changes in peritoneal cavity leukocyte populations after the treatment of peritoneal surface dissemination of gastrointestinal, fallopian tube, ovarian, and primary peritoneal cancers with talimogene laherparepvec, we will perform multi-color flow cytometry analysis on peritoneal lavage fluid from patients at baseline (prior to seroconversion dose on C1D1), prior to treatment on C2D1, and on C4D1. If the subject comes off treatment mid cycle, there will be an additional plasma sample at the time of disease progression or off treatment. Immune cells will be stained with fluorescent antibodies specific for markers of major leukocyte subsets as commonly performed by the [name] Lab.

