3.0 STUDY DESIGN

3.1 Study Description

This is a non-randomized, open-label Phase I trial in patients with Stage IV peritoneal surface dissemination from gastrointestinal, fallopian tube, ovarian, or primary peritoneal tumors enrolled at Duke Cancer Institute and select external collaborating institutions. All subjects will complete an extensive medical history, baseline physical examination and clinical assessment to ensure subject eligibility requirements (see Eligibility Criteria for details) within 4 weeks of starting study drug. All eligible patients must have a peritoneal catheter placed prior to the initiation of therapy. All patients will receive an initial seroconversion dose of talimogene laherparepvec 4×10^6 PFU on Cycle 1 Day 1 to enable seroconversion as described in the currently approved treatment protocol for the treatment of cutaneous melanoma. Three weeks (+3 days) after the initial seroconversion dose, patients will receive talimogene laherparepvec at the dose level for the cohort for which they are enrolled every 2 weeks (± 3 days) for up to 4 doses. The length of the first cycle is 5 weeks and subsequent cycles are 2 weeks in duration.

- Enrolled subjects are defined as subjects who give informed consent.
- Screen failures are defined as subjects who give informed consent and do not meet eligibility criteria.
- Accrued subjects are defined as subjects who give informed consent and meet eligibility criteria.
 - Withdrawal: Subject accrued but later withdrawn from the study, either before or after receiving a study drug.
 - Evaluable: In the Dose Escalation Cohort, subjects who are accrued, received study treatment, and completed the first cycle of safety assessments or have dose limiting toxicity (DLT) which is study treatment related that precludes completing the full cycle of assessments will be considered evaluable for DLT. All subjects (in Dose Escalation and Dose Expansion) who are accrued and receive any study treatment will be considered evaluable for toxicity. All subjects in Dose Escalation and Dose Expansion who are accrued and receive any study treatment will be considered evaluable for efficacy.
 - Non-evaluable: In the Dose Escalation Cohort, subjects who accrued but did not complete the first cycle of safety assessments due to reasons other than study treatment-

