related toxicity (e.g. disease progression or inter-current illness) are considered non-evaluable for DLT. All subjects (in Dose Escalation and Dose Expansion) who are accrued, received study treatment but did not complete initial restaging due to reasons other than disease progression (e.g. inter-current illness) will be considered non-evaluable for efficacy.

Table 3.1 Proposed Dose Levels

Dose Level	No. Evaluable Subjects	TVEC IP, once every 2 weeks x 4 doses*
Dose Escalation		
1 (starting dose)	3-6	4×10^6
2	3-6	4×10^7
3	3-6	4×10^8
Dose Expansion		
Expanded Cohort	6	MTD

*All patients will receive an initial seroconversion dose of 4×10^6 PFU. The first dose at each of these Dose Levels will be administered 3 weeks (+3 days) after the initial seroconversion dose, and then be given every 2 weeks \pm 3 days for a total of 4 doses at each Dose Level (in addition to the initial seroconversion dose, which all patients will receive).

Using a standard '3+3' dose escalation design, there are up to three dose levels that may be explored. See Table 3.1 for the dosing scheme.

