9.0 STATISTICAL ANALYSIS

9.1 General Analysis Considerations

Up to 30 subjects will be enrolled and treated. The intent to treat population is defined as all subjects who receive treatment with talimogene laherparepvec at the MTD.

The per protocol population is defined as all subjects who:

- Undergo treatment with talimogene laherparepvec
- Fulfill all inclusion and exclusion criteria
- Are evaluable for the primary efficacy criterion, TTP

The safety population consists of all the subjects who receive talimogene laherparepvec for whom safety data is available. All safety analyses will be carried out on this population.

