9.1.1 Statistical Methods

- The statistical analyses will be performed on the intent to treat, the per protocol, and safety populations.
- Statistical analyses will be only descriptive.
- Descriptive statistics will be provided according to the nature of variables
- Mean, standard deviation, minimum and maximum, median and quartiles will be provided for quantitative variables.
- Percent and frequencies will be provided for qualitative variables.
- Time to events will be illustrated with survival curves using the Kaplan-Meier method.
- Confidence intervals will be constructed from outcomes intent.

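### Response is estimated in a per-protocol set that may drop treated subjects with no restaging, so the reported rate is likely, though not certain, to be too high

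*Combined protocol and SAP*

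**What the plan says.** **Set and estimator (Section 9.1.4).** The set is named first: "Patients in the per protocol population will be classified as responder or non-responder". For the estimator, the same sentence then specifies that "the proportion of patients exhibiting response at trial closure by any criteria will be estimated by the 90% confidence interval". The interval method is not named. The next paragraph of the same section assigns TTP to the intent-to-treat population.

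**Per-protocol definition (Section 9.1).** Besides receiving the drug, a subject must satisfy "Fulfill all inclusion and exclusion criteria" and "Are evaluable for the primary efficacy criterion, TTP". What makes a subject evaluable for TTP is not stated.

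**Efficacy evaluability (Section 3.1).** Under the evaluable heading, all subjects "who are accrued and receive any study treatment will be considered evaluable for efficacy". Under the non-evaluable heading, treated subjects who "did not complete initial restaging due to reasons other than disease progression (e.g. inter-current illness) will be considered non-evaluable for efficacy".

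**General statements.** Section 9.1.1: "The statistical analyses will be performed on the intent to treat, the per protocol, and safety populations". Section 9.1.4: "For all efficacy endpoints, analyses will be performed overall and in the patients treated at the MTD". Section 9.1 defines the intent-to-treat set as subjects treated at the MTD, not all treated subjects.

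**Timing.** Section 5.3 places the on-treatment restaging at C4D14. Section 5.4 adds scans and tumor markers every 12 weeks for subjects who finish or stop treatment without progression, until progression or new anti-cancer therapy.

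**The concern.** The response proportion is the figure that later studies will take from this trial's efficacy data. Its denominator depends on an undefined term, and the only written rule that makes a treated subject non-evaluable for efficacy turns on whether restaging took place. A subject who leaves before any restaging usually has neither scan nor marker evidence, because Section 5.5 ties markers to baseline and restaging. Such a subject will seldom be called a responder. Removing these subjects from the denominator, instead of counting them as non-responders, would normally raise the rate.

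Because the two evaluability rules conflict, the denominator could also be settled after the results are known. No section specifies a response rate in all treated subjects, or says how to count a subject with no assessment.

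**Working it through.** **1. The plan's own precision figure.** The documents give no expected response rate, loss rate or precision for response. The nearest figure is in Section 9.1.3: a proportion in 12 subjects is estimated to within 0.237 with 90% confidence. The normal approximation at p = 0.5 reproduces it: 1.645 × √(0.25/12) = 0.2374. With 9 subjects the same formula gives 1.645 × √(0.25/9) = 0.274.

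**2. When restaging first occurs.** Cycle 1 lasts 5 weeks and later cycles 2 weeks, so C4D14 falls on day 35 + 14 + 14 + 14 = 77. Some losses before then are plausible: Section 1.1 cites a median survival of six months in this disease.

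**3. Who leaves under the stricter Section 3.1 rule.**
- Removed: subjects with no initial restaging because of withdrawal, intercurrent illness, death without documented progression, loss to follow-up, or new therapy started first.
- Kept: subjects not restaged because they progressed.
- Can be kept: subjects who stop early without progression and are first restaged in the 12-weekly follow-up. Section 3.1 does not tie initial restaging to C4D14.

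**4. Size.** Let N be the number treated, m the number dropped, r the responders among those kept, and x the number among the dropped who would have been classed as responders.
- Per-protocol rate: r/(N-m).
- All-treated rate: (r+x)/N.
- With x = 0, the ratio of the first to the second is N/(N-m), its largest value.

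The values of r and m below are assumptions. N = 12 is the intent-to-treat size in Section 9.1.3, 24 is the synopsis maximum, and 30 is the Section 9.1 maximum. Intervals are exact (Clopper-Pearson) 90%, and x = 0.

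| N | r | m | All treated | Per protocol | Factor |
|---|---|---|---|---|---|
| 12 | 3 | 1 | 25.0% (7.2-52.7) | 27.3% (7.9-56.4) | 1.09 |
| 12 | 3 | 2 | 25.0% (7.2-52.7) | 30.0% (8.7-60.7) | 1.20 |
| 12 | 3 | 3 | 25.0% (7.2-52.7) | 33.3% (9.8-65.5) | 1.33 |
| 12 | 3 | 4 | 25.0% (7.2-52.7) | 37.5% (11.1-71.1) | 1.50 |
| 24 | 5 | 4 | 20.8% (8.6-38.9) | 25.0% (10.4-45.6) | 1.20 |
| 24 | 5 | 6 | 20.8% (8.6-38.9) | 27.8% (11.6-49.8) | 1.33 |
| 30 | 5 | 6 | 16.7% (6.8-31.9) | 20.8% (8.6-38.9) | 1.25 |

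**5. Direction.** The per-protocol rate exceeds the all-treated rate only when x < r·m/(N-m). For r = 3, N = 12 and m = 3, the break-even is 3 × 3/9 = 1. One responder among the three dropped removes the bias (4/12 = 33.3%). If all three had responded, the all-treated rate would be 6/12 = 50%, above the per-protocol 33.3%.

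**The case against.** A reader might infer that nobody can respond without a restaging scan, so that each exclusion can only raise the rate. The documents do not support that. Section 5.7 and the synopsis let the treating physician judge response on a composite that includes symptoms and abdominal girth, Section 9.1.4 accepts any criterion, and girth is measured on Day 1 of every cycle. An unscanned subject can be called a responder. Upward bias is the likely direction only.

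A reader might also infer that everyone who stops early is removed. As shown above, subjects who progressed, and those first scanned in follow-up, can stay in.

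A stronger objection is that the link from the per-protocol set to the stricter Section 3.1 rule is itself an inference. The other rule in that section makes every treated subject evaluable. Section 9.1.4 also censors for TTP those who withdraw, are lost, die or start other treatment, so they could be regarded as evaluable for TTP. On that reading few or none leave. This stands, and it means that the denominator is unsettled. It does not make the text adequate, since either reading can be defended.

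Nor is it right to say that response will be computed only in the per-protocol set, because Section 9.1.1 lists three populations. That general sentence still supplies no all-treated response rate: the intent-to-treat set covers MTD subjects only, and the safety set is assigned to safety analyses. Reporting overall and at the MTD names dose groups and does not return dropped subjects to the count.

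Finally, the endpoint is exploratory, the statistics are descriptive, no decision rule uses the rate, and the illustrated shifts lie inside the intervals. All of this is correct and limits the consequence to reporting.

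**Conclusion.** The concern holds in a qualified form. Section 9.1.4 assigns response to a set conditioned on undefined evaluability, and Section 3.1 gives contradictory rules for who is evaluable. If the stricter rule applies, the reported rate is likely to be biased upward, by a factor of at most N/(N-m). With 3 of 12 dropped, 3 responders among those kept and none among the dropped, the rate rises by 8.3 percentage points, from 25.0% to 33.3%.

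This rests on two assumptions that the documents do not settle: how many subjects would be lost, and that those lost respond less often than those kept. If the more inclusive rule applies, the restaging-related bias largely disappears. A claim that the bias is greatest at the most toxic dose would be a further inference, since the documents give no loss rates by dose.

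The safety objective and MTD determination are unaffected. The change is worth making because the response rate will be read as a preliminary efficacy signal and the correction is cheap.

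**What to change.** 1. In Section 9.1.4, estimate the response proportion in all subjects who received any study drug, overall and at the MTD, with an exact 90% interval. Count a subject with no post-baseline response assessment by any criterion as a non-responder. A subject assessed clinically or by marker without a scan keeps that classification.
2. Keep the per-protocol proportion as a supportive analysis, and list the reason for each missing restaging.
3. Reconcile the two efficacy-evaluability rules in Section 3.1, and define in Section 9.1 what makes a subject evaluable for TTP.

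The cost is one sentence in Section 9.1.4 plus the clarifications in Sections 3.1 and 9.1. No new data are needed. The downside is a slightly lower headline response rate, because an early leaver who was never assessed counts as a failure.

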5.7 Tumor Assessments

Tumor Response will be assessed via a composite of a variety of endpoints and ultimately, the treating physician's judgment and assessment of these endpoints. Given the variability in clinical presentation of these malignancies, radiographic imaging findings, and baseline laboratory values, assessing tumor response may take into account clinical features, radiographic response, laboratory response, and clinical endpoints.

Clinical features may include, but are not limited to, performance status (ECOG or Karnofsky score), abdominal girth, development of bowel obstructions felt to be resulting from peritoneal tumor deposits, development of clinically-evident ascites, and frequency of paracenteses due to malignant ascites.

Radiographic response may be used to track those patients who have radiographically-evaluable tumor deposits at baseline, which may be prone to following with serial imaging. For a subset of these patients who have such radiographically-evaluable lesions, it may be possible to assess tumor response based on serial imaging (CT chest/abdomen/pelvis with and without contrast and/or MRI or PET imaging), using RECIST version 1.1 criteria. Some peritoneal surface malignancies will not be amenable to grading using RECIST version 1.1 criteria. However, there are other imaging scoring systems such as the SPAAT[11] Score or a modified peritoneal cancer index based upon multi-detector CT imaging [12] which may be helpful in establishing a radiographic determination of tumor response to therapy. The exact method of analyzing a given patient's imaging will depend on that patient's radiographic findings at baseline, and the radiologist's determination of the best method of following serial changes in imaging.

For those patients who have elevated blood tumor markers at baseline, following the response of these tumor markers to therapy will factor into assessing tumor response to therapy.

Clinical endpoints of progression-free survival and overall survival will also be used to assess response to therapy.

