Given the heterogeneity in presentations of patients with peritoneal surface malignancies, patients will likely be followed by a composite of a variety of the above endpoints, and these endpoints may be different from patient to patient. However, for a given patient, all attempts will be made to use the same method for tumor assessment at every assessment timepoint. Progressive disease (PD) may manifest in findings such as significant clinical progression, evidence of 20% increase in disease seen on

imaging, and/or increase in tumor marker by 20% over baseline. Response may manifest in findings such as improvement in clinical symptoms, evidence of 30% decrease in measurable tumor burden, and/or 30% decrease in tumor marker from baseline.

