Endoscopy, laparoscopy: The utilization of these techniques for objective tumor evaluation is not advised. However, they can be useful to confirm complete pathological response when biopsies are obtained or to determine relapse in trials where recurrence following complete response or surgical resection is an endpoint.

Tumor markers: Tumor markers alone cannot be used to assess objective tumor response. If markers are initially above the upper normal limit, however, they must normalize for a patient to be considered in complete response. Because tumor markers are disease specific, instructions for their measurement should be incorporated into protocols on a disease specific basis. Specific guidelines for both CA-125 response (in recurrent ovarian cancer) and PSA response (in recurrent prostate cancer), have been published. In addition, the Gynecologic Cancer Intergroup has developed CA125 progression criteria which are to be integrated with objective tumor assessment for use in first-line trials in ovarian cancer.

Cytology, histology: These techniques can be used to differentiate between PR and CR in rare cases if required by protocol (for example, residual lesions in tumor types such as germ cell tumors,

where known residual benign tumors can remain). When effusions are known to be a potential adverse effect of treatment (e.g. with certain taxane compounds or angiogenesis inhibitors), the cytological confirmation of the neoplastic origin of any effusion that appears or worsens during treatment can be considered if the measurable tumor has met criteria for response or stable disease in order to differentiate between response (or stable disease) and progressive disease.

Response Criteria

Evaluation of Target Lesions

- Complete Response (CR): Disappearance of all target lesions. Any pathological lymph nodes (whether target or non-target) must have reduction in short axis to <10 mm.
- Partial Response (PR): At least a 30% decrease in the sum of diameters of target lesions, taking as reference the baseline sum diameters.
- Progressive Disease (PD): At least a 20% increase in the sum of diameters of target lesions, taking as reference the smallest sum on study (this includes the baseline sum if that is the smallest on study). In addition to the relative increase of 20%, the sum must also demonstrate an absolute increase of at least 5 mm. (Note: the appearance of one or more new lesions is also considered progression).

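### Response is counted at trial closure and by any criteria: the time point is not tied to an assessment, and marker-only or symptom-only responses can be pooled with RECIST responses

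*Combined protocol and SAP*

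**What the plan says.** The quantity in Section 9.1.4 (Exploratory Endpoints) is "the proportion of patients exhibiting response at trial closure by any criteria", in the per-protocol population, and it "will be estimated by the 90% confidence interval". The section adds that methods are specific to the patient, and that "In the subset of patients with radiographically measurable disease RECIST 1.1 criteria will be used". Confirmation, by laparoscopy, is planned only after a radiographic or marker complete response.

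Section 5.7 (Tumor Assessments) supplies the criteria. "Tumor Response will be assessed via a composite of a variety of endpoints and ultimately" rests on the judgment of the treating physician. Its examples of response are clinical improvement, a 30% fall in measurable tumor burden and a "30% decrease in tumor marker from baseline", joined by and/or. Its examples of progression are clinical worsening, a 20% increase on imaging and an "increase in tumor marker by 20% over baseline", joined in the same way.

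Appendix A (RECIST 1.1) says "Tumor markers alone cannot be used to assess objective tumor response" and describes best overall response. Section 2.3 lists the size and duration of tumor response as the first exploratory objective.

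**The concern.** Two features make the response proportion hard to interpret.

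The first is timing. Closure is an event in the life of the trial, whereas response is observed at a patient's own visits. If status at closure is what counts, a response that has been lost by then disappears from the numerator, and many patients will have no current scan or marker on that date.

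The second is content. One proportion can combine RECIST responses, marker falls and symptom improvement. A reader could not tell how much of it is objective response or compare it with a RECIST rate from another trial. A patient with discordant findings could be a responder in this table and a progressor in the time-to-progression analysis.

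**Working it through.** **No planned figure to reproduce.** The plan gives no target, sample size or precision for the response proportion. The neighboring figure in Section 9.1.3 does reproduce: 1.645 × √(0.25/12) = 0.237, the stated half-width for a proportion in 12 patients.

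**Time point.** Set side by side:
- Section 5.3 and the Study Calendar (Appendix C): one planned restaging, at C4D14 (±3 days).
- Section 5.4 and Calendar notes 2 and 17: scans and markers then follow every 12 weeks, or as indicated, until progression or new anti-cancer therapy.
- Section 11.8: study completion is trial-wide, when all subjects have finished follow-up and the data are clean.
- Section 9.1.4: response is counted at closure.

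Take a patient who responds at C4D14 and progresses at the first 12-weekly visit. Tumor assessment stops there. At closure this patient is not in response. Under best overall response the same patient is a responder with a measurable duration. A closure count gives no duration, which Section 2.3 asks for.

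Appendix A asks protocols to state whether post-treatment assessments count toward best overall response and how new therapy before progression is handled. Section 9.1.4 answers neither for response; its censoring rule for alternative treatment applies only to time to progression. The first question matters because Section 5.3 ends the Treatment Period at the last dose, so C4D14 already lies after it.

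**Criteria.** Section 4.1 admits patients on an elevated marker without measurable disease, so marker-only responses are to be expected. Suppose the marker is down 30% and imaging is up 20%: one example of response and one of progression are both met, and no section says which governs.

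**Illustrations (assumed inputs).**

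*Pooling.* If imaging, marker and clinical response each occur in 10% of patients, the proportion meeting any of them is 10% if nested, 1 − 0.9³ = 27.1% if independent, and 30% if disjoint.

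*Chance marker falls.* Assume a log-normal marker with no true change, one baseline value and one follow-up value. The SD of the log ratio is √2 × √ln(1 + CV²), and the chance of a fall of at least 30% is Φ(ln 0.7 / SD). At CV 20%, SD = 0.280, z = −0.357/0.280 = −1.27, and the chance is 10.1%.

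| Assumed CV | One follow-up | Either of two follow-ups (simulated) |
|---|---|---|
| 10% | 0.6% | 1.1% |
| 15% | 4.5% | 8.1% |
| 20% | 10.1% | 17.1% |
| 30% | 19.5% | 30.5% |

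*One patient's weight.* The exact 90% (Clopper-Pearson) limits are the 5% point of Beta(x, n−x+1) and the 95% point of Beta(x+1, n−x). With an illustrative n = 12, x = 1 gives 0.004 to 0.339 and x = 2 gives 0.030 to 0.438. The size of the per-protocol population is not stated.

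**The case against.** The plan can be read more kindly. Section 9.1.4 makes the method patient-specific and calls for RECIST 1.1 where disease is measurable. Section 5.7 intends one method per patient throughout, words its thresholds as examples and leaves the decision to the physician, because peritoneal disease presents so variably. Any criteria may then mean whichever method suits that patient. The endpoint is exploratory, the analyses are descriptive, and no dose or stopping rule uses this proportion.

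Most of this stands, and it defeats two stronger readings.

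- *A single marker dip makes a responder despite imaging progression.* A reader might infer this, but no section says it. It is a reading that the text permits, and it sits poorly with status at closure, since a dip that has reversed by then would not count.
- *Marker progression measured from baseline contradicts the nadir rule in Section 5.7.1.* That rule governs the sum of target-lesion diameters; no section sets a nadir reference for markers. Changing the reference would also have a cost. Under the same noise assumptions, with two follow-ups and no true change, false marker progression rises from 16%, 30%, 39% and 48% (from baseline) to 23%, 41%, 52% and 63% (from nadir) at CVs of 10%, 15%, 20% and 30%. Letting a marker rise alone cancel an imaging response would carry the same noise into the response rate.

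The kinder reading does not repair the time point. It also still yields one proportion that mixes marker-based with RECIST-based responses, and physician judgment names a decider without giving a rule for discordant findings.

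**Conclusion.** The point holds for the time point and for the pooling of criteria. Response at closure does not match the assessment schedule, the stated objective or the best overall response described in Appendix A. The any-criteria wording permits marker-only responses in a rate that readers may take as objective response, contrary to the Appendix A statement on markers, and leaves discordant findings unclassified.

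The effect on the reported rate cannot be computed from the documents. The CVs, the 10% rates and n = 12 are illustrative; at that size each reclassified patient shifts the estimate by 1/12, about 8 percentage points. The consequence is confined to exploratory efficacy. The change is still worth making before results are seen, because Section 9.1.4 expects these data to inform on efficacy and reports the rate with a confidence interval.

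**What to change.** In Section 9.1.4:

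1. Define response as best overall response from first dose until progression or new anti-cancer therapy, with C4D14 as the main time point. State that assessments after the last dose count.
2. Beside the physician composite, report two separate rates: RECIST 1.1 response in patients with measurable disease, and marker response in patients with an elevated baseline marker.
3. State that a patient with RECIST progression at a visit is not a responder at that visit.
4. Correct the pointer for response methods from Section 5.6 (Adverse Event Assessment) to Section 5.7.

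Leave the baseline reference for marker progression as it is, and do not let a marker rise alone override response.

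Cost: SAP wording and two more table rows, with no added visits, samples or patients. The composite rate may come out lower where RECIST progression disqualifies a patient; counting responses that later relapse works in the other direction. Taking the best of several visits also gives marker noise more chances, as the two-follow-up column shows, which is a reason to keep C4D14 as the main time point and the marker rate separate.
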